The number and quality of social contacts on each day of the previous week will be measured ([name] et al., 2016), including detailed questions about social activities as developed in the on-going PGfAR VOLUME (on volunteering in mental health) and including questions of the Time Use Survey ([name] et al., 2016). In addition to the questions from the Time Use Survey we ask about the price of each activity in order to estimate what activities would be reasonable to offer during the intervention.

Quality of life and loneliness assessments

The researchers will collect the information on subjective quality of life (MANSA, [name] et al., 1999) health-related quality of life (EQ-5D-3L, Rabin et al., 2014), and ICEpop CAPability measure for Adults, which is a measure of capability for the general adult (18+) population for use in economic evaluation (ICECAP-A, Al-Janabi et al., 2013). Unlike most profile measures used in economic evaluations, the ICECAP-A focuses on wellbeing defined in a broader sense, rather than health. We also assess subjective loneliness through UCLA-8 loneliness scale (Hays and DiMatteo, 1987) and Global Rating of Loneliness.

During the baseline interview, researchers will ascertain whether patients meet the inclusion criterion of having "quality of life score 5 or less" using the MANSA ([name] et al., 1999). If yes, they will be invited to participate in the intervention.

Randomisation procedures

Patients will be randomised to either the intervention or control. The allocation ratio will be 2:1 in favour of the intervention. Randomisation will be stratified by NHS Trust, ensuring balance between

groups in the patient numbers from each NHS Trust. Blocked randomisation with a block size of $m=3$ will be used within each stratum. A fixed block size of $m=3$ is appropriate in this trial as the feasibility of intervention and study procedures is of primary interest and not intervention effects. Should blocked randomisation be used in the full trial a variable block size would be utilised.

The randomization will be carried out remotely by the Pragmatic Clinical Trials Unit at Queen Mary, University of London. The PCTU will inform the research team of the results of the allocation by secure email using a password protected file.

Intervention

a. Type and frequency of meetings

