This applies to both the intervention and control groups. All participants from the intervention group, and half of the control participants, chosen at random, will complete the follow-up. Participants will fill out the same questionnaires as during baseline assessment:

- Sociodemographic information;
- Client Service Receipt Inventory, (CSRI, Beecham and Knapp, 2011);
- Positive And Negative Syndrome Scale (PANSS, Kay, 1991);
- Clinical Assessment Interview For Negative Symptoms (CAINS, Kring et al., 2013);
- Social Contacts Assessment (SCA, [name] et al., 2016);
- Time Use Survey (TUS, [name] et al., 2016);
- Manchester Short Assessment of Quality of Life questionnaire (MANSA, [name] et al., 1999);
- EQ-5D-3L (Rabin et al., 2014);
- ICECAP-A (Al-Janabi et al., 2013);
- Global rating of Loneliness;
- UCLA Loneliness Scale (Hays and DiMatteo, 1987);

Client Satisfaction Questionnaire (Attkinsson and Zwick, 1982) will be added at the follow up assessment in order to evaluate satisfaction with the intervention.

In-depth (qualitative) interviews

Clinician and patient interviews will be conducted to assess their experiences of the intervention. All interviews will be audio-recorded and facilitated by a researcher using a topic guide. Patient interviews will take place at the end of their intervention, and clinician interviews will be conducted when they have completed interventions for all of their patients. Interviews will last between 45-60 minutes and will take place in quiet rooms across NHS sites, quiet rooms at the participating Universities or in patients' homes. We plan to conduct the interviews with 32 patients who took part in the intervention and with 8 out of 16 control participants. We will have sufficient time (9 month allocated to the study) and resources (we can rely on the help from CSOs) to conduct, record and analyse those interviews.

Payment to participants:

Patients taking part in baseline and post-intervention interviews will be offered £15 cash or voucher as a reimbursement for their time for each interview (maximum £30). Clinician participants will not be reimbursed for their time as the intervention sessions will take place during their working hours. The commitment required is not likely to have a significant effect on their working time and the participation of the clinicians will be discussed with their line managers and team leads.

Adherence to manual

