6.1.1 Patient identification

Mental health professionals with different roles who fit the eligibility criteria will be asked to participate. They will be approached by email, letter, phone or in person.

Patients on community team caseloads will be screened for eligibility by clinical teams. Clinicians will contact patients (by phone or face-to-face) and if patients verbally agree to meet a researcher, they will be invited to the baseline interviews with researchers. The research team will not contact patients unless they have received permission from clinicians or participants from the previous part of the project to do so. Once patients verbally agree to meet a researcher, the clinicians will share permission and patients' contacts with researchers through encrypted email networks, phone or face-to-face meetings. The researchers will then contact patients face to face or via phone, offering to send participant information sheets via post or directly providing them if the meeting is face to face. The

baseline interview could follow during the same session or patients will be allowed one week to think about their participation.

The eligibility will be then confirmed during the baseline interviews by the research team with reference to the criterion of "5 or less score on the MANSA "

If patients meet all the inclusion criteria, they will be invited to participate in the intervention and in the follow-up quantitative and qualitative interviews. The interviews will take place within NHS facilities, quiet rooms at the participating Universities or at patients' home based on patients' preferences.

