6.5 Future Study

If following this feasibility trial there will be no major amendments to the intervention or research procedures, we will propose to the independent Programme Steering Group that: a) we will continue recruitment for a full hypothesis testing randomised controlled trial; b) we will use participant data from the feasibility trial (WP4) in the subsequent full randomised controlled trial (Work Package 5).

If the independent Programme Steering Group will approve our proposals we will submit the protocol for the full randomised controlled trial to the ethics committee as a major amendment.

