7 STATISTICS AND DATA ANALYSIS

Objective 1 and 2:

We will gain further experience of how the intervention is delivered in NHS settings and will carry out qualitative interviews with patients and clinicians. We will discuss with the steering group and the LEAP findings from qualitative material from audio-recordings of sessions, open ended sections of the fidelity instrument and clinician and patient interviews with the steering group in order to decide on whether any further modifications to the intervention or the training manual are required.

Objective 3:

In order to assess the feasibility of recruitment and randomisation procedures, the number of screened participants, eligible participants and of those who refused participation or were not approached will be recorded. The number of participants who withdraw from the study will also be recorded. Screening, recruitment and retention will be presented as rates with 95% confidence intervals. Descriptive statistics (mean (sd) for continuous variables and count (%) for nominal) will be reported for socio-demographic data and on social contacts, social activities, quality of life and symptoms scores. Changes in number of social contacts, time spent in social activities, quality of life and symptoms following the intervention will be reported as estimates with 95% confidence intervals. No efficacy related statistical tests will be conducted.

Objective 4:

We will estimate excess treatment costs more in detail through obtaining information from clinical records on the number of sessions offered and whether additional sessions need to be offered because of non-attendance. This will be analysed through descriptive statistics.

We will explore two different methods to calculate cost-effectiveness of the intervention using the EQ-5D-3L and the ICECAP-A. We will explore ease of administration of both instruments through interviews with patients and analyse frequency and type of missing data through descriptive statistics. The final decision on what instrument to be adopted will be made by the programme management group following discussion with the steering group and the lived experience advisory panel.

Objective 5:

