7.2 Sample size calculation

A total of 12 clinicians and 48 patients will be recruited across all sites, with 32 randomised to the intervention (3 patients per clinician). Randomisation services will be provided by the Pragmatic Clinical Trials Unit (PCTU) at QMUL. This number of participants was chosen in order to allow exploratory testing of the intervention in a small number of patients for further refinement and specification before randomised controlled trial in a larger number of patients. Clinicians will be purposively sampled in order to recruit clinicians with different roles and therefore assess feasibility of training and delivering the intervention.

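### Limiting the quantitative follow-up to a random half of the 16 controls discards half of the control outcomes for no stated reason; following up all 48 patients is a cheap improvement.

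*Protocol*

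**What the plan says.** The restriction stands in protocol section 6, under the heading for the follow-up quantitative interviews and just before the list of questionnaires: "All participants from the intervention group, and half of the control participants, chosen at random, will complete the follow-up". The in-depth interviews have their own paragraph and their own numbers: "We plan to conduct the interviews with 32 patients who took part in the intervention and with 8 out of 16 control participants". The restriction on the questionnaires is therefore a separate statement.

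The numbers come from section 7.2 ("A total of 12 clinicians and 48 patients will be recruited across all sites, with 32 randomised to the intervention (3 patients per clinician") and from the randomisation paragraph in section 6 ("The allocation ratio will be 2:1 in favour of the intervention").

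Three other places bear on the point:
- Section 6.1.1 says of patients who meet all the inclusion criteria that "they will be invited to participate in the intervention and in the follow-up quantitative and qualitative interviews". It mentions no sub-sample.
- Section 7, Objective 3, says "Screening, recruitment and retention will be presented as rates with 95% confidence intervals" and "The number of participants who withdraw from the study will also be recorded". It also plans estimates of change in the outcomes with 95% confidence intervals, and it rules out efficacy testing.
- Section 6.5 says that, if no major amendments prove necessary, the team will propose to the independent steering group that "we will use participant data from the feasibility trial (WP4) in the subsequent full randomised controlled trial (Work Package 5".

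**The concern.** Sub-sampling controls makes sense for long qualitative interviews, where a few informants can be enough. It is harder to justify for the questionnaires, because every patient left out removes an outcome from a small arm. The protocol gives no reason for doing so.

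Three things are at stake:
- **Control-arm estimates.** Changes in social contacts, activities, quality of life and symptoms would be described in controls from 8 people at most. The same holds for the follow-up service-use data, and for the missing-data patterns of EQ-5D-3L and ICECAP-A that section 6 (Economic evaluation) wants to examine.
- **Feasibility of following up controls.** How many controls complete the full battery is useful to know before a full trial, and it would be learned from 8 people.
- **Possible reuse.** If WP4 data enter the full trial, half of the WP4 controls would have baseline data and no outcome. The decision on reuse comes after WP4 ends, when the end-of-intervention assessment can no longer be made.

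**Working it through.** **Inputs.** From the protocol: 48 patients and 32 to the intervention (section 7.2); 2:1 allocation and follow-up of all intervention patients and half of the controls (section 6). The protocol gives no expected completion rate, so 75%, 87.5% and 100% are illustrative assumptions.

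**1. Reproducing the protocol's numbers.** 48 × 2/3 = 32 intervention; 48 × 1/3 = 16 control; 16 / 2 = 8 controls followed up. This agrees with the stated 32 and with the 8 of 16 given for the in-depth interviews. There is no power calculation to reproduce. Before any drop-out, at most 32 + 8 = 40 patients can have outcomes, and the followed-up ratio is 32:8 = 4:1 instead of 2:1.

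**2. Between-arm difference in mean change, in SD units.** SE = √(1/n_int + 1/n_ctrl), assuming equal SDs.
- 32 v 8: √(1/32 + 1/8) = 0.395; t-based 95% half-width 0.80 SD.
- 32 v 16: √(1/32 + 1/16) = 0.306; t-based 95% half-width 0.62 SD.
- Ratio of SEs: 0.395 / 0.306 = 1.29. Ratio of variances: 1.67. Information retained: 6.4 / 10.67 = 60%, so 40% is lost.

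**3. Mean change in the control arm alone.** Half-width = t(0.975, n−1) / √n.
- n = 8: 0.84 SD.
- n = 16: 0.53 SD.

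**4. Follow-up completion in controls (exact Clopper-Pearson 95% intervals).**

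| Assumed completion | 8 selected | 16 selected |
|---|---|---|
| 75% | 6/8: 35% to 97% | 12/16: 48% to 93% |
| 87.5% | 7/8: 47% to 99.7% | 14/16: 62% to 98% |
| 100% | 8/8: 63% to 100% | 16/16: 79% to 100% |

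**5. Completion over both arms.** At 87.5%, 35/40 gives 73% to 96% and 42/48 gives 75% to 95%. The overall rate hardly changes in precision, so the loss is confined to the control arm.

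**6. Reuse in the full trial.** 16 − 8 = 8 of the 16 randomised controls (50%) would have no outcome by design.

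**The case against.** The best defence is that this is an explicit, randomised choice in a feasibility study. Section 6 says that feasibility, not intervention effects, is the main interest, and section 7 plans no efficacy tests. It does not clearly specify a between-arm contrast either. All of that stands: the cost is precision, not power or validity, and the between-arm figures apply only if such a difference is estimated.

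A reader might infer that the sub-sampling ruins the retention estimate. The protocol does not support that. Random selection leaves completion among those selected unbiased, the 32 intervention patients are unaffected, and withdrawals are recorded with no restriction to the follow-up sample. Section 7 does not promise retention by arm. A ceiling of 40/48 = 83% would arise only if retention meant follow-up over all randomised patients, a definition the protocol does not adopt.

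A reader might also infer that the reuse plan in section 6.5 is defeated. It is not. Reuse depends on there being no major amendments, on steering group approval and on an ethics amendment. The planned gap is missing completely at random, so the 32 + 8 outcomes could be carried forward without bias from this source.

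Nor is section 6.1.1 a strong contradiction. Read literally, it also invites every eligible patient to the intervention, which 2:1 randomisation excludes. It is loose recruitment wording.

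Finally, the extra work is more than a payment: each follow-up is a full battery that includes PANSS and CAINS. None of these points supplies a reason for leaving out 8 controls.

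**Conclusion.** The point holds as a cheap improvement, not as a flaw that biases or invalidates the study. The quantitative follow-up discards half of the control outcomes without a stated reason. The SE of any between-arm difference rises by 29% (0.395 against 0.306 SD), and the half-width for mean change in controls rises from 0.53 to 0.84 SD. Knowledge of control completion rests on 8 people. The sub-sampling also undermines the conditional reuse of WP4 data, because 8 of 16 randomised controls would have no outcome and the gap cannot be closed afterwards.

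These figures assume equal SDs in the two arms and no drop-out; the completion intervals rest on assumed rates, with the range shown.

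**What to change.** In section 6, change the sentence so that all 48 randomised patients have the quantitative follow-up, and keep the random half of controls (8 of 16) for the in-depth interviews only. Align section 6.1.1 so that it says which patients are invited to which follow-up.

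The cost is a wording change, up to 8 more full assessment batteries (including PANSS and CAINS) by the existing researchers, and up to 8 × £15 = £120 in reimbursement.

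If the sub-sample is kept, compute questionnaire completion over the 40 patients selected for follow-up and withdrawal over all 48. State in section 6.5 that controls who were not selected contribute no outcome to the full trial.

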Study aims and objectives	
Aim: Using the developed manual and training as developed in WPs 2 and 3, we will conduct a feasibility trial to prepare the full trial in WP5.
 
The specific objectives are to:
 
 1. Further specify the intervention, intervention manual and training module in preparation for the full randomised controlled trial; 2. Gain further and more systematic practical experience with the intervention in the NHS; 3. Check the feasibility of recruitment and randomisation procedures; 4. Refine the methods for assessing the costs of the intervention including the resources required for the training; 5. Explore further which professional groups should deliver the intervention in the full trial, and 6. Test methods for assessing adherence to the manual.

FUNDING AND SUPPORT IN KIND

FUNDER(S) (Names and contact details of ALL organisations providing funding and/or support in kind for this trial)	FINANCIAL AND NON FINANCIALSUPPORT GIVEN
National Institute for Health Research	Programme Grant for Applied Research
East London NHS Foundation Trust (supported by Noclor)	Study sponsorship
East London NHS Foundation Trust	NHS treatment and support costs. Permission to conduct study on Trust premises with Trust employees and patients
Tees, Esk & Wear Valleys NHS Foundation Trust	NHS treatment and support costs. Permission to conduct study on Trust premises with Trust employees and patients
Devon Partnership NHS Trust	NHS treatment and support costs. Permission to conduct study on Trust premises with Trust employees and patients
Oxford Health NHS Foundation Trust	NHS treatment and support costs. Permission to conduct study on Trust premises with Trust employees and patients
Queen Mary University of London	Substantive employer of Chief Investigator

ROLE OF STUDY SPONSOR AND FUNDER

East London NHS Foundation Trust the sponsor, Noclor Research Support Service is acting on behalf of East London NHS Foundation Trust to assume overall responsibility for the initiation and management of the study. The National Institute of Health Research has provided funding for the study.

ROLES AND RESPONSIBILITIES OF TRIAL MANAGEMENT COMMITTEES/GROUPS & INDIVIDUALS

Study Management Committees

The main roles and responsibilities of each committee are outlined below:

- Programme Management Group

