Knowledge about the local context will be helped by a list of possible local options for low cost activities in the local area available to the patient that involve contacts with other people. This list will be provided by the research team. Clinicians will also be expected to and supported in obtaining a good knowledge about the options and encouraged to network in the given community to generate more options for relevant activities. Learning progress will be assessed during the training and in the subsequent supervision, provided by senior members of the research team, which will be organised flexibly in order to identify the ideal frequency. At the end of the case studies, clinicians who have delivered the intervention will receive an in-depth interview and will be encouraged to provide suggestions for further refinement of the intervention, of the training and of the supervision arrangements.

e. Further support of clinicians

Clinicians will receive updates on changes in options for activities from the local research team and from participating clinicians themselves through networking. They will also be supervised through regular phone calls (at least once a month or more if and as required) either locally or centrally from the study team in London.

Recording of the intervention sessions

For each clinician, we will aim to audio-record three interventions sessions (if the patients consent to this). They will be helpful to understand what are the topics and activities discussed during the intervention sessions and to identify ways to help motivation and commitment of patients to social activities in order to help specify training guidelines and obtain examples to be used for a training package.

Control group

Patients in the control group will be provided with comprehensive information about local options for social activities by the researcher. This group is intended to control for the provision of information and non-specific attention through a professional in addition to routine care. Also, the mere provision of information should be regarded as good practice independent of additional targeted interventions, so that patients in the control group should receive it too.

The usual treatment, including care-coordination, medication, and psychological therapies, will not be affected, neither in the intervention nor in the control group.

Follow-up quantitative interviews with a researcher

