6.4 Withdrawal criteria

During the consent process, researchers will ensure that participants (both patients and clinicians) are aware of their right to decline participation at any stage of the research and that withdrawing participation will not affect their treatment or rights. Participants will be able to ask that their data is eliminated before the end of February 2019.

For WP4, if patients withdraw from the intervention, then the research team will ask permission to contact them to take part in the post-intervention qualitative interview in order to capture valuable information regarding reasons for withdrawal, which might be associated with the intervention. This will be explained to patients during the consent process and on the information sheet, and patients' decisions to not be contacted for the post-intervention interview will be respected.

If a participant wishes to withdraw from the study, researchers will record date of withdrawal and reason(s) for withdrawal.

Clinicians delivering the intervention will monitor the capacity throughout the intervention duration. If a participant, who has given informed consent, loses capacity to consent during the study. The participant would be withdrawn from the study. Identifiable data or tissue already collected with consent would be retained and used in the study.

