We plan to have different professionals delivering the intervention during the feasibility trial (e.g. psychiatrists, nurses, occupational therapists, senior psychologists and psychology graduates). The final decision on which type of professionals will be chosen to deliver the intervention will be made by the programme management group following discussion with the steering group and the lived experience advisory group. The discussion will be based on data from the adherence checklist and from the interviews with patients and clinicians.

Objective 6:

The data collected using the adherence checklist will be triangulated with audio-recordings of sessions to test whether there is concordance and the less expensive method (i.e. adherence checklist) is appropriate to measure fidelity in the trial. The audio-recordings will be rated by independent evaluators in the research team according to the same domains as found in the adherence checklist. We will calculate correlation rates through correlation statistics and report to the steering group. A final decision will then be made on whether to amend the current adherence checklist or use alternative methods to assess fidelity in the trial.

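### Clinician interviews are tied to completing all patients and no exit interview is planned for clinicians who stop, so that strand of evidence for Objectives 1, 2 and 5 comes from completers

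*Protocol*

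**What the plan says.** **When clinicians are interviewed.** Protocol section 6, In-depth (qualitative) interviews: "clinician interviews will be conducted when they have completed interventions for all of their patients". Section 6, Training of clinicians, is worded more loosely: "At the end of the case studies, clinicians who have delivered the intervention will receive an in-depth interview".

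**Who may withdraw, and what follows.** Section 6.4 has researchers ensure that "participants (both patients and clinicians) are aware of their right to decline participation at any stage of the research". The invitation to an interview after withdrawal is narrower: "if patients withdraw from the intervention, then the research team will ask permission to contact them to take part in the post-intervention qualitative interview". Its stated purpose is to learn why people withdraw, since the reasons may lie in the intervention. Section 6.4 also says: "If a participant wishes to withdraw from the study, researchers will record date of withdrawal and reason(s) for withdrawal".

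**What the evidence is for.** Objective 5 in the Study Summary is to "Explore further which professional groups should deliver the intervention in the full trial". Section 7 gives the basis for that decision: "The discussion will be based on data from the adherence checklist and from the interviews with patients and clinicians". Under Objectives 1 and 2, section 7 also uses clinician interviews, with other qualitative material, to decide whether the intervention or training manual needs changing.

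**Numbers.** Section 7.2 plans 12 clinicians, purposively sampled across roles, and 48 patients, of whom 32 go to the intervention at a stated 3 patients per clinician. Section 7, Objective 5, names five professions as examples.

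**The concern.** The only stated time for a clinician's interview is when that clinician has finished with all of their patients. A clinician who changes post, runs short of time or loses confidence in the intervention after one or two patients does not reach that point, and no other section schedules an interview for them. Section 6.4 accepts for patients that people who stop have something particular to tell the study. It does not carry this over to clinicians, although the same section lets them withdraw.

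What is at stake is qualitative evidence, not an estimate or an error rate. A feasibility trial is meant to find out whether NHS staff can sustain the intervention alongside their ordinary work. Section 6 (Payment to participants) expects the effect on clinicians' working time to be small. A clinician who stops for lack of time would be direct evidence on that expectation, and under the stated timing would not be interviewed.

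**Working it through.** **1. The plan's own numbers.** Inputs are from sections 6 (Randomisation procedures) and 7.2.
- Intervention patients at 2:1 allocation: 48 × 2/3 = 32, as stated.
- Clinicians needed at 3 patients each: 32 / 3 = 10.67, so 11, against 12 stated.
- In the other direction: 32 / 12 = 2.67 patients per clinician, rounded to 3 in the text (12 × 3 = 36).

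The figures agree to within rounding. No power, significance level or effect size is stated, and none bears on this point. Most clinicians have two or three patients to finish before the stated interview time.

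**2. The passages side by side, for a clinician who stops early.**

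| Source | Available if the clinician stops? | Named as an Objective 5 input? |
|---|---|---|
| Clinician interview (section 6) | Not under the stated timing | Yes |
| Interview after withdrawal (section 6.4) | No, written for patients | For clinicians, not provided |
| Date and reasons for withdrawal (section 6.4) | Yes, if participant includes clinicians | No |
| Adherence checklist | Yes, for sessions already delivered | Yes |
| Interviews with that clinician's patients | Yes | Yes |

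The clinician's own account is lost as an interview, and what is logged about the stop is not named for the decision.

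**3. How much one interview weighs.**
- Average per profession over the five examples: 12 / 5 = 2.4. Over four professions (assumed): 12 / 4 = 3.
- One lost interview is 1/3 = 33% of a group of three, 1/2 = 50% of a group of two, and 1/12 = 8% of all clinician interviews.

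**4. How likely a loss is.** The protocol gives no clinician dropout rate, so a range d is assumed, with clinicians taken as independent.
- Expected losses: 12 × d.
- Chance that at least one of 12 stops: 1 − (1 − d)^12.
- Chance that some profession has no completing clinician: 1 − Π(1 − d^s), where s is the number of clinicians in each profession.

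| Assumed dropout d | Expected losses | At least one of 12 stops | Some profession has no completer, split 3/3/2/2/2 | Same, split 3/3/3/3 |
|---|---|---|---|---|
| 5% | 0.6 | 46% | 0.8% | 0.05% |
| 10% | 1.2 | 72% | 3.2% | 0.4% |
| 20% | 2.4 | 93% | 12.9% | 3.2% |
| 30% | 3.6 | 99% | 28.7% | 10.4% |

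Losing at least one clinician interview is quite likely even at modest dropout. Losing every clinician interview from a profession is unlikely unless dropout is high.

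**The case against.** The strongest reply is that early stopping leaves traces elsewhere. Three sources are named for Objective 5, and only one is the clinician interview. Section 6 plans interviews with the 32 intervention patients, and section 6.4 seeks them even from patients who withdraw. Session records and checklists exist up to the point of stopping. Supervision calls take place at least monthly, so the team would usually know of a clinician in difficulty. Section 6.4 records date and reasons, and section 7, Objective 3, counts participants who withdraw. The sentence in Training of clinicians asks only that the clinician has delivered the intervention, so the stricter sentence can be read as a matter of timing rather than a bar. Objective 5 is exploratory and is settled by committee discussion.

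Much of this stands. A reader might infer that the choice of profession rests only on clinicians who stayed, or that a profession unable to sustain delivery could not be told from one that can. The documents do not support either: patient interviews, truncated session records and logged reasons all remain. A reader might also count clinicians whose last patient starts late, because the six-month intervention must fit within the nine-month study. That is a separate timetable matter, not selection by who continues.

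What the reply does not remove is narrower. A logged reason is not a topic-guide interview of 45 to 60 minutes. Neither logged reasons nor clinician retention is named for Objective 5. The looser sentence still places the interview at the end and does not say that it covers a clinician who stops partway.

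**Conclusion.** The point holds in a limited form and is minor. As written, the clinician-interview part of the evidence for Objectives 1, 2 and 5 comes from clinicians who complete with all of their patients. The interview after withdrawal is for patients only, and recorded withdrawal reasons are not an input to the choice of profession. The other two Objective 5 sources still inform that choice.

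The size is modest: one interview out of 2 or 3 for the profession concerned. This rests on an assumed even split of 12 clinicians over four or five professions. The chance of at least one such loss, 46% to 99%, rests on assumed dropout of 5% to 30%. No sample size, power or error rate is affected. Because these rules are fixed in the protocol, this is not something left to a statistical analysis plan.

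**What to change.** - **Section 6, In-depth (qualitative) interviews:** hold the clinician interview when the clinician completes their last patient or stops delivering the intervention, whichever comes first. Align the sentence under Training of clinicians.
- **Section 6.4:** extend the request for an interview after withdrawal to clinicians, and state that recording of date and reasons covers them.
- **Section 7, Objective 5:** add clinician retention and recorded reasons for stopping, by profession, to the material for the decision. With 2 or 3 clinicians per profession these should be plain counts.

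The cost is small changes to the protocol, the clinician information sheet and the topic guide. There would be at most 12 clinician interviews, one per clinician. Some clinicians who stop will decline, so the gap will narrow rather than close.
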